## 7.2 Flow Chart

The number of enrolled participants and participants in the mITT and Per-protocol populations will be presented in a flow chart by treatment group.

## 8 Analysis of study objectives

### 8.1 Primary Objective (PO1)

To assess if simultaneous use of a vibration and cool pack device (Buzzy®) and an electronic game before and during intramuscular vaccination will reduce risk for presyncope or syncope after vaccination in adolescents. This information is collected in CRF forms: “Buzzy® Form”, “Electronic Game Form”, “Presyncope or Syncope Form (EVENT FORM)”, and “Post Vaccination Questions” (Modified BDRI (PostVax)). The proportion of adolescents with presyncope or syncope as determined by the modified BDRI or witnessed presyncope or syncope after vaccination will be compared between the control and intervention groups using a chi-square test.

- *Research hypothesis: The Buzzy® and electronic game intervention will be at least 50% effective at reducing risk for post-vaccination presyncope or syncope compared with control.*  
This objective will be assessed using a chi-square test with the alpha level set at 0.05 (2-sided).

### 8.2 Secondary Objectives

1. **Secondary Objective (SO1):** To compare the change in state anxiety score for adolescents before and after vaccination in the control group to the intervention group.

This information is collected in CRF Forms: “Youth Momentary Anxiety Checklist (YMAC)” and “Anxiety – Youth - 11-17.” The categorical change in the anxiety score (positive, negative, and no change) in pre- and post- vaccination state anxiety will be presented by group in a tabular format. A comparison of the two study groups will be made using a Mantel-Haenszel statistic (row mean scores difference with standardized midranks scores [modified ridit scores]). Descriptive statistics (e.g., mean, 95% CI, min, max) of the pre- minus post- vaccination state anxiety will be presented by group and compared using Mann-Whitney U/Wilcoxon rank-sum test.

**Secondary Outcome Measure SOM 1.1:** Categorical change (positive, negative, no change) in pre- and post- vaccination state anxiety.

- Assess frequency and proportions of adolescents reporting a categorical change (positive, negative, no change) in their overall score for anxiety according to state anxiety questionnaire, before and after vaccination, by intervention group and age group, as appropriate.

**Secondary Outcome Measure SOM 1.2:** Numeric change (mean and 95% confidence interval (CI)) in pre- minus post- vaccination state anxiety.

- Assess overall mean score and standard deviation of adolescents’ anxiety scores according to state anxiety questionnaire, before and after vaccination, by intervention group and by age group, as appropriate.

2. **Secondary Objective (SO2):** To compare the change in injection-site pain after vaccination of adolescents in the control group to the intervention group. This information is collected in CRF forms: "Post-Vaccine Form" and "Wong-Baker Faces Pain Scale." The following four outcomes will be compared between groups using a chi-square test or a logistic regression model to control for covariates:

- The proportion of adolescents reporting an injection site pain score  $\geq 2$ , on the Wong-Baker Faces Pain Scale©,  $\leq 1$  minute following vaccination
- The proportion of adolescents reporting an injection site pain score  $\geq 4$ , on the Wong-Baker Faces Pain Scale©,  $\leq 1$  minute following vaccination
- The proportion of adolescents reporting an injection site pain score  $\geq 2$ , on the Wong-Baker Faces Pain Scale©, at (approximately) 10 minutes following vaccination
- The proportion of adolescents reporting an injection site pain score  $\geq 4$ , on the Wong-Baker Faces Pain Scale©, at (approximately) 10 minutes following vaccination.

Descriptive statistics (e.g., mean, 95% CI, min, max) of injection-site pain scores on the Wong-Baker Faces Pain Scale© at  $\leq 1$  and minute and at (approximately) 10 minutes following vaccination will be presented by group and compared using Mann-Whitney U/Wilcoxon rank-sum test.

3. **Secondary Objective (SO3):** To assess the acceptability of the intervention among the adolescents based on their positive or negative responses for each survey item. A descriptive breakdown of the responses will be presented in tabular format. This information is collected in CRF form "Buzzy® and Electronic Game Acceptability Scale":

1. How much did you like having Buzzy® on your arm(s) during the shot(s)? (Disliked very much; Disliked a little; Neither liked or disliked; Liked a little; Liked very much; Not Sure)
2. How difficult or easy was holding or having Buzzy® held on your arm during the shot(s)? (Very difficult; Somewhat difficult; Neither difficult nor easy; Somewhat easy; Very easy; Not Sure)
3. How comfortable or uncomfortable was Buzzy® on your arm(s) during the shot(s)? (Very uncomfortable; Somewhat uncomfortable; Neither comfortable nor uncomfortable; Somewhat comfortable; Very comfortable; Not Sure)
4. Did the cold temperature of Buzzy® bother you? (No; Yes; Not Sure)
5. Did the vibration of Buzzy® bother you? (No; Yes; Not Sure)
6. If you had the choice would you like to use Buzzy® again when receiving shots? (No; Yes; Not Sure)
7. Write below anything else you want us to know about your experience with Buzzy®. (free text)
8. How much did you like playing a game during the shot(s)? (Disliked very much; Disliked a little; Neither liked or disliked; Liked a little; Liked very much; Not Sure)
9. How difficult or easy was it to select and play the game? (Very difficult; Somewhat difficult; Neither difficult nor easy; Somewhat easy; Very easy; Not Sure)
10. How comfortable or uncomfortable were you playing a game when receiving shots? (Very uncomfortable; Somewhat uncomfortable; Neither comfortable nor uncomfortable; Somewhat comfortable; Very comfortable; Not Sure)

11. If you had the choice would you like to play a game again when receiving shots? (No; Yes; Not Sure)
12. Write below anything else you want us to know about your experience with playing a game. (free text)

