7 STUDY SCHEDULE, PROCEDURES, & EVALUATIONS

7.1 Schedule of Events

Adolescents meeting the proposed eligibility criteria will be recruited and if enrolled the subject could spend up to two hours in the clinic. Written permission for the adolescent to participate will be obtained from parent(s)/guardian(s) prior to conducting any study procedures. Written or verbal assent, depending on the age of the adolescent, will also be obtained. **Table 1** describes the proposed schedule of study visits.

Table 1: Schedule of Study Events:

Procedure	Pre-Vaccination Day 1	Vaccination Day 1	Post-Vaccination Day 1
Informed consent / Assent	X		
Inclusion/Exclusion	X		
Demographics	X		
Medical history	X		
Concomitant medications	X		
Beverage and food intake assessment on day of vaccination	X		
PROMIS Pediatric Anxiety Short Form	X		
Needle phobia assessment	X		
State Anxiety assessment	X		X ¹ (20 minutes)
Record/obtain physical measures (height and weight) and vital signs (blood pressure and pulse and baseline pain assessment done per usual care)	X		
Randomization	X		

Simultaneous Buzzy® and electronic game intervention or usual care	X		
Administer vaccines (not a study procedure)		X	
Injection site pain assessment			X (within 1-3 and at 10 minutes)
Presyncope symptoms assessment			X (15 minutes)
Acceptability Assessment			X (20 minutes)

¹ Complete prior to acceptability assessment

Visit 1, Study Day 1 Clinic Visit Prevaccination Assessments

- Obtain parent(s)/guardian(s) permission by written informed consent
- Review and confirm study eligibility (Section 4.1 and 4.2)
- Obtain medical history
- Obtain demographic data
- Obtain concomitant medication use within one week of enrollment
- Record height and weight and vital signs (blood pressure and pulse) from the medical record. Obtain measures if not already taken and recorded at clinic intake. Record baseline pain assessment if determined as part of clinical care
- Complete beverage and food intake assessment for the day of vaccination
- Complete the needle phobia assessment
- Complete the general anxiety assessment and the state anxiety assessment
- Randomize study participant to one of the two study arms
- Administer assigned study intervention if randomized to that group

Visit 1, Study Day 1 Clinic Visit Vaccination

- Vaccines administered by clinic staff (Not a study procedure)
- Vaccines administered as usual care will be recorded by study team

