7.7 Anxiety

Prior to vaccination the study coordinator will have each subject complete a questionnaire to assess generalized anxiety using the Patient Reported Outcome Measurement Information System (PROMIS) Pediatric Anxiety Short Form v2.0 8a instrument for adolescents (11-17 years) to categorize their overall degree of anxiety.⁴⁰

Participants will also complete a questionnaire specifically designed for this study to measure state anxiety both prior to and 20 minutes following vaccination. State anxiety is defined as an unpleasant emotional arousal in face of threatening demands or dangers.^{41,42}

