8.2.4 Secondary and Exploratory Objectives**Secondary Objective (SO 1):**

The first secondary objective is to compare the change in state anxiety score for adolescents before and after vaccination in the control group to the intervention group. The categorical change in the anxiety score (positive, negative, and no change) in pre- and post- vaccination state anxiety will be presented by group in a tabular format. A comparison of the two study groups will be made using a Mantel-Haenszel statistic (row mean scores difference with standardized midranks scores [modified ridit scores]). Descriptive statistics (e.g., mean, 95% CI, min, max) of the pre- minus post- vaccination state anxiety will be presented by group and compared using Mann-Whitney U/Wilcoxon rank-sum test.

Secondary Objective Measure (SO 2):

The second secondary objective is to compare the change in injection-site pain after vaccination of adolescents in the control group to the intervention group. The following four outcomes will be compared between groups using a chi-square test or a logistic regression model to control for covariates:

- The proportion of adolescents reporting an injection site pain score ≥ 2 , on the Wong-Baker Faces Pain Scale©, ≤ 1 minute following vaccination
- The proportion of adolescents reporting an injection site pain score ≥ 4 , on the Wong-Baker Faces Pain Scale©, ≤ 1 minute following vaccination
- The proportion of adolescents reporting an injection site pain score ≥ 2 , on the Wong-Baker Faces Pain Scale©, at (approximately) 10 minutes following vaccination
- The proportion of adolescents reporting an injection site pain score ≥ 4 , on the Wong-Baker Faces Pain Scale©, at (approximately) 10 minutes following vaccination.

Descriptive statistics (e.g., mean, 95% CI , min, max) of injection-site pain scores on the Wong-Baker Faces Pain Scale© at ≤ 1 and minute and at (approximately) 10 minutes following vaccination will be presented by group and compared using Mann-Whitney U/Wilcoxon rank-sum test.

Secondary Objective Measure (SO 3):

The third secondary objective is to assess the acceptability of the intervention among the adolescents based on their positive or negative responses for each survey item. The groups will be compared for each survey item using a chi-square test.

Exploratory Objective (EO 1):

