#### 3.2 Secondary Outcome Measures (SOM):

- a) SOM 1.1: Categorical change (positive, negative, no change) in pre- and post- vaccination state anxiety.
- b) SOM 1.2: Numeric change (mean and 95% CI) in pre- minus post- vaccination state anxiety.
- c) SOM 2.1: Mean injection-site pain scores on the Wong-Baker Faces Pain Scale© at  $\leq 1$  minute following vaccination.
- d) SOM 2.2: Proportion of adolescents reporting an injection site pain score  $\geq 2$ , on the Wong-Baker Faces Pain Scale©,  $\leq 1$  minute following vaccination.
- e) SOM 2.3: Proportion of adolescents reporting an injection site pain score  $\geq 4$ , on the Wong-Baker Faces Pain Scale©,  $\leq 1$  minute following vaccination.
- f) SOM 2.4: Mean injection-site pain scores on the Wong-Baker Faces Pain Scale© at (approximately) 10 minutes following vaccination.
- g) SOM 2.5: Proportion of adolescents reporting an injection site pain score  $\geq 2$ , on the Wong-Baker Faces Pain Scale©, at (approximately) 10 minutes following vaccination.
- h) SOM 2.6: Proportion of adolescents reporting an injection site pain score  $\geq 4$ , on the Wong-Baker Faces Pain Scale©, at (approximately) 10 minutes following vaccination.
- i) SOM 3: Proportion of adolescents reporting positive and negative perceptions about their vaccination experience will be determined for each survey item.

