#### 4.3 Sample Size and Power Estimation

The study has approximately 82.0% power to reject the null hypothesis of no difference in the proportion of adolescents with presyncope or syncope after vaccination in the intervention (vibration and cool pack device [Buzzy®] and an electronic game) group compared to the control (usual care) group based on a two-side alpha 0.05 chi-square test with N=160 per group. This assumes that the proportion of adolescents with presyncope or syncope after vaccination will be 25% in the control group and 2-fold lower (12.5%) in the intervention group. This assumption is based on a review of the literature and expert opinion. We plan to enroll approximately 340 adolescents for this study with the assumption of a 5% drop out rate, thus providing at least 160 subjects per group to have approximately 82% power.

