#### 4.4 Randomization

Participants will be randomized (1:1) to receive either Buzzy® and electronic game or the control using a permuted block randomization scheme. A minimum of 170 participants will be enrolled in the intervention group and 170 in the control group. The project statistician at Duke University will generate randomization schemes, which will be uploaded to REDCap. The randomization schedule will not be available to the study staff, so the next randomization allocation will not be known before randomization occurs. Following confirmation of study eligibility criteria during Visit 1, participant randomization will be through REDCap with treatment allocation recorded on the CRF.

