### 5.2 Analytic Issues

No adjustments will be made to the alpha level (two-sided alpha=0.05) for the study objectives described below.

The primary and exploratory objective analyses will be performed in the Modified intent-to-treat (mITT) and Per-protocol populations, or only the mITT population if no subject is excluded from the per protocol population. No adjustments will be made to the alpha level (two-sided alpha=0.05) for the study objectives described below.

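### State anxiety (SO1) is tested on the raw change without baseline adjustment, and no between-arm estimate with a confidence interval is promised: valid, but probably less precise

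*SAP*

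**What the plan says.** Protocol 7.7 has participants complete "a questionnaire specifically designed for this study to measure state anxiety both prior to and 20 minutes following vaccination". In the pre-vaccination list of Protocol 7.1, the item "Complete the general anxiety assessment and the state anxiety assessment" stands above the randomisation step, and Table 1 has the same order. SAP 4.4 describes the allocation: "Participants will be randomized (1:1) to receive either Buzzy® and electronic game or the control using a permuted block randomization scheme".

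SAP 3.2 defines SOM 1.2 as "Numeric change (mean and 95% CI) in pre- minus post- vaccination state anxiety". For the analysis, SAP 8.2 says that descriptive statistics of "pre- minus post- vaccination state anxiety will be presented by group and compared using Mann-Whitney U/Wilcoxon rank-sum test". Protocol 8.2.4 has the same plan: "Descriptive statistics (e.g., mean, 95% CI, min, max) of the pre- minus post- vaccination state anxiety will be presented by group", followed by the same test. SAP 8.2 also asks for means and SDs of the scores before and after vaccination, by arm and by age group where appropriate. SOM 1.1 (positive, negative or no change) has its own Mantel-Haenszel row-mean-score test.

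For SO1, neither document uses the pre-vaccination score as a covariate or commits to a between-arm difference with a confidence interval. Elsewhere the plan does more. SO2 allows a logistic model with covariates for the four pain proportions, and exploratory objective EO2 promises a relative risk with a 95% CI.

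**The concern.** Two things are left unused or unsaid.

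- **Precision.** A raw change score subtracts the whole baseline value whatever its correlation with the post-vaccination score. When that correlation is modest, the subtraction adds noise. A model with the baseline as covariate estimates how much to subtract, and the trial already collects the score it needs.
- **Reporting.** The outcome is defined as a mean change, but the test is rank-based. Its p-value does not correspond to the difference between the two reported means, and no effect estimate is prespecified to go with it.

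Protocol 1.2 names anxiety as one of the two routes, with injection-site pain, by which the intervention is meant to work. If the anxiety comparison is unclear, readers will need the size of the difference and its uncertainty, and the plan does not promise either. There is no bias at stake.

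**Working it through.** **The plan's own power figure.** SAP 4.3 states: "The study has approximately 82.0% power to reject the null hypothesis of no difference". This is for the primary outcome, with 25% versus 12.5%, 160 per group and two-sided alpha 0.05. With pooled variance under the null:

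- mean proportion = 0.1875; √(2 × 0.1875 × 0.8125) = 0.5520; √(0.25 × 0.75 + 0.125 × 0.875) = 0.5449
- z = (0.125 × √160 − 1.96 × 0.5520) / 0.5449 = 0.916, so power = 82.0%

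The figure reproduces. It says nothing about SO1, for which the documents give no power, SD, pre-post correlation, score range or target effect. Only 160 per arm and alpha 0.05 below come from the documents; the other inputs are assumptions.

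**Variance, against a mean-based analysis of change.** Let s0 and s1 be the pre and post SDs and ρ their correlation.

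- Var(change) = s1² + s0² − 2ρ·s1·s0
- Var(ANCOVA) = s1²(1 − ρ²)
- Difference = (s0 − ρ·s1)², which is never negative, so the ratio never exceeds 1. With equal SDs it is (1 + ρ)/2.

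Ratio ANCOVA / change:

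| s1/s0 | ρ = 0.3 | 0.5 | 0.7 | 0.9 |
|---|---|---|---|---|
| 0.8 | 0.50 | 0.57 | 0.63 | 0.61 |
| 1.0 | 0.65 | 0.75 | 0.85 | 0.95 |
| 1.25 | 0.78 | 0.89 | 0.98 | 0.95 |

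Example: s1/s0 = 0.8 and ρ = 0.5 give 0.48/0.84 = 0.57. At s1/s0 = 1.25 and ρ = 0.8 the ratio is 0.5625/0.5625 = 1.00, so there is no gain. With equal SDs the confidence interval width ratios are 0.81, 0.87, 0.92 and 0.97. At ρ = 0.5, ANCOVA with 0.75 × 160 = 120 per arm is as precise as mean change with 160.

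**Power, against the planned rank-sum test.** Simulation with 160 per arm, 2000 runs per cell and an effect of 0.30 of the pre SD on the post score. ANCOVA used HC3 standard errors. In the floored case a latent normal score was rounded to integers and cut at 0, with 35% at the floor before and 55% after in controls, and the effect was applied before flooring. Entries are rank-sum versus ANCOVA, in %:

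| Scores | ρ = 0.3 | 0.5 | 0.7 | 0.9 |
|---|---|---|---|---|
| Normal | 60 vs 80 | 76 vs 87 | 91 vs 96 | 100 vs 100 |
| Integer with floor | 29 vs 61 | 34 vs 66 | 46 vs 78 | 68 vs 98 |
| t, 5 df | 66 vs 79 | 81 vs 87 | 96 vs 96 | 100 vs 100 |
| t, 3 df | 80 vs 81 | 93 vs 87 | 99.5 vs 96 | 100 vs 99.8 |

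The Monte Carlo SE is at most √(0.25/2000) = 1.1 points. With no effect and ρ = 0.5, rank-sum rejected 4.9 to 5.4% and ANCOVA 4.2 to 5.8%, so both are valid.

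**Closed-form check, normal scores, equal SDs, ρ = 0.5.** ANCOVA: SE = √(2/160) × √0.75 = 0.0968, and 0.30/0.0968 − 1.96 = 1.14, which gives 87%. Rank-sum, with efficiency 0.955 relative to the t-test: SE = √(2/160) × √(1/0.955) = 0.1144, and 0.30/0.1144 − 1.96 = 0.66, which gives 75%. Both agree with the simulation.

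**Second simulation, separately programmed.** It used a different floor and ordinary standard errors, and showed the same pattern. At ρ = 0.5, rank-sum versus ANCOVA was 74 versus 86% (normal), 40 versus 74% (floored) and 95 versus 88% (t, 3 df).

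**The case against.** The strongest reply is that this is an efficiency preference on a valid test of one secondary objective, and that its size rests on an unseen instrument. That is fair as far as it goes. The most striking gaps come from an assumed floor, and with t(3) tails the planned test wins from ρ = 0.5 upwards until both are near 100%. This is why the conclusion is only that the test is probably less precise. Tails that heavy are unlikely for a bounded checklist score, while a floor is plausible.

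A second reply is that readers can derive a difference. The arms are independent and mean changes with 95% CIs are specified by arm, so an unadjusted difference and an approximate interval follow. SOM 1.1 adds the distribution of categorical change. Both points stand, but a contrast left to the reader is not a prespecified estimate, and it would still be unadjusted. The primary analysis in SAP 8.1 also stops at a test, so the reporting gap is not confined to SO1.

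Third, the case for linear rather than rank-based adjustment is not settled. In the second simulation, ANCOVA on ranks had 98% power with t(3) scores at ρ = 0.5, against 95% for rank-sum and 88% for linear ANCOVA. It matched linear ANCOVA with a floor (74% each) and lost a little under normality (84 versus 86%). A rank-based model is therefore defensible. Linear ANCOVA has the advantage of an estimate on the score scale, which fits an outcome defined as a mean.

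Last, it adds a test to a plan that says "No adjustments will be made to the alpha level (two-sided alpha=0.05) for the study objectives described below". Naming one analysis as primary for SOM 1.2 answers most of that.

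**Conclusion.** The concern holds. SO1 is analysed by a valid test on the raw change, without a baseline covariate that is already collected and without a committed between-arm estimate.

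The reporting gap rests on the text alone. The precision loss depends on assumed SDs, correlation, score shape and effect. Under normal scores it costs about 20 points of power at ρ = 0.3 and 5 at ρ = 0.7. With a floor it costs about 30 points over ρ = 0.3 to 0.9. With very heavy tails it vanishes or reverses.

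This should be changed, but it does not threaten the trial: the primary result, the sample size and type I error are not affected.

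**What to change.** In SAP 8.2 and Protocol 8.2.4, prespecify one primary analysis for SOM 1.2: ANCOVA of post-vaccination state anxiety on arm and pre-vaccination state anxiety, reporting the adjusted mean difference with a robust (HC3) 95% CI. This still answers the objective as worded, because with the baseline in the model the arm effect is the same, apart from sign, whether the outcome is the post score or the pre-minus-post change.

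Keep the rank-sum test on change, with a Hodges-Lehmann shift and 95% CI, and the SOM 1.1 comparison as supportive analyses, reported whatever the ANCOVA shows. Do not add a rule that switches models after looking at the data. If the statistician prefers a rank-based or ordinal adjusted model, it should be fixed in advance in the same way.

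The cost is one paragraph in the SAP and matching text in the protocol, with no new data. The change should be dated before anyone sees anxiety results by arm; if that has already happened, the adjusted analysis should be labelled post hoc.
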